The conduct of these studies will involve 20 human subjects. All subjects will be adults able to give informed consent. Subjects will be enrolled without regard to gender or race. However, an effort will be made for an enrolled population composed of at least 50% females and ~50% members of an ethnic minority according to the demographic characteristics of the Philadelphia area. Children will not be enrolled. All patients will be recruited from the Hospital of the University of Pennsylvania or the Penn Presbyterian Medical Center. The study involves various tests (cardiac MRI with gadolinium, arterial tonometry, ambulatory blood pressure / pulse wave analysis measurements, a blood draw) and the administration of ISMN and ascorbic acid therapy.

Potential Risks: There is minimal risk to the subjects. Potential risks are associated with Targeting Central Hemodynamics in CKD Pilot Study Protocol Version 003, February 15, 2016

the study tests, the study interventions (pharmacologic therapy) and potential breaches in confidentiality.

- (1) **Cardiac MRI:** The non-invasive nature and the lack of ionizing radiation make the risks associated with MRI small. A MRI scan requires the participant to be in a partially enclosed space inside the scanner. Some people may find this to be uncomfortable. Claustrophobia is an exclusion criterion for the study. The MRI scanner produces different types of noises during a scan. Participants are special earplugs to reduce the noise. A MRI scanner has a strong magnet which attracts certain metals. If anyone has these types of metal in their body, the MRI's strong magnetic field can cause them to move which may cause injury. Subjects will be thoroughly screened for the presence of body metal and excluded from the study if they are unable to safely undergo a cardiac MRI.

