Wave reflections can be markedly reduced by organic nitrates, which dilate middle-sized muscular arteries even at doses that do not substantially reduce brachial blood pressure. Our overarching hypothesis is that reducing arterial wave reflections with organic nitrates will reduce LV hypertrophy (a precursor to HF), fibrosis and improve myocardial function in subjects with CKD, independently of blood pressure reduction. Our ultimate goal is to perform an RO1-funded double-blind, parallel-arm, placebo-controlled randomized clinical trial that will enroll patients with CKD and randomize them to either sustained-release isosorbide mononitrate therapy (SR-ISMN) or placebo for 24 weeks.

In this R56-funded study, we aim to obtain key preliminary data for an RO1 resubmission to accomplish a phase IIb randomized controlled trial to test our hypothesis. We wish to obtain: (1) preliminary data regarding the variability in the change of our endpoints in response to our intervention in this specific population; (2) Preliminary data regarding the effects of ISMN on blood pressure vs. wave reflections at different doses; (3) Data supporting the feasibility and local expertise to implement a biomarker discovery approach using proteomics. Our specific aims are:

PRIMARY AIMS: to assess the variability in the response and to perform a dose-response assessment in the degree of change in central hemodynamics and cardiac endpoints with Targeting Central Hemodynamics in CKD Pilot Study
Protocol Version 003, February 15, 2016

ISMN therapy in this population. We propose to administer 3 different doses of SR-ISMN (30, 60 and 120 mg of SR ISMN daily) to 20 subjects with CKD, in order to accomplish the following co-primary aims:

- 1a. To assess the variability in the change in **LV mass** with ISMN administration (**in order to support aim 1a of our eventual RO1-funded trial**). LV mass will be measured with steady-state free precession cardiac MRI.
- 1b. To assess the variability in changes in **diffuse myocardial fibrosis** with ISMN administration, using T1-mapping MRI techniques.⁵⁻¹²
- 1c. To assess the variability in changes in **myocardial systolic and diastolic function** with ISMN administration, assessed via systolic strain (measured with displacement encoded MRI, DENSE) and early diastolic mitral annular velocity (measured with tissue Doppler echocardiography), respectively.

SECONDARY AIMs:

[figure not shown]

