Subjects will be recruited from referrals as well as medical record searches (PennSeek). We will enroll adults (age 18 or older) who meet the following criteria:

Inclusion criteria: (1) Chronic kidney disease stage 3 (defined as an estimated glomerular filtration rate [GFR] of 30-59 ml/min/1.73m²), estimated by the CRIC GFR equation⁴³ (2) An elevated left ventricular mass index (defined as >60 g/m^{1.7} in women and 80 g/m^{1.7} in men)³⁸ or LV posterior wall thickness⁴⁴ >1.4 cm documented in a clinically indicated echocardiographic or MRI examination within the previous 24 months; (3) Stable medical therapy as defined by no addition, removal or change in dosage >100% of ACE

inhibitors, angiotensin receptor blockers, beta-blockers, or calcium channel blockers for >30 days; (4) Current therapy with an ACE inhibitor, hydralazine or a statin, all of which have been shown to reduce nitrate tolerance.⁴⁵⁻⁵³

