Blood Draw: Blood samples will be obtained in order to measure serum creatinine and hematocrit prior to each cardiac MRI. In addition, samples will be centrifuged and frozen at -80 degrees C to perform proteomics analysis using the Somascan platform, which measures ~1300 plasma proteins. We will also collect a spot urine sample (~50 cc) in every study visit.

C.5. Run-in phase and ISMN initiation

Subjects will first undergo a run-in phase to assess within subject responses to ISMN at doses of 30 mg, 60 mg and 120 mg daily (with or without ascorbic acid), which will be better powered than between-arm comparisons. Half the subjects will be randomly assigned to receive ascorbic acid (500 mg by mouth three times daily).

- After baseline assessments, ISMN will be initiated at a dose of 30 mg daily (with or without ascorbic acid).
- **1-week visit:** Subjects will undergo a brief visit for peripheral, central BP and arterial stiffness measurements (arterial tonometry and VaSera device measurements) after ~1 week (5-9 days). ISMN will be increased to 60 mg daily. Blood (20 cc) and urine (~50 cc) will also be sampled and frozen.
- **2-week visit:** Subjects will undergo a brief visit for peripheral, central BP and arterial stiffness measurements (arterial tonometry and VaSera device

measurements) after ~1 week (5-9 days). ISMN will be increased to 120 mg daily. Blood (20 cc) and urine (~50 cc) will also be sampled and frozen.

- **3-week visit:** Subjects will undergo a brief visit for peripheral, central BP and arterial stiffness measurements (arterial tonometry and VaSera device measurements) after ~1 week (5-9 days). Subjects will also undergo a Doppler echocardiogram during this visit. A 24 hour ambulatory BP monitoring Blood (20 cc) and urine (~50 cc) will also be sampled and frozen.

In all cases, up-titration will occur only if:

- (1) Resting supine systolic blood pressure is ≥ 95 mmHg;
- (2) There is no evidence of orthostatic hypotension (decrease ≥ 20 mmHg in systolic or ≥ 10 mmHg in diastolic blood pressure within 3 minutes of standing);⁶³
- (3) The subject is not experiencing dizziness, vertigo, or other symptoms that, in the opinion of the investigator, may be due to the vasoactive effect of the drugs.

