If the drug is not tolerated, subjects will be discontinued from the study. After completion of the run-in phase, subjects will be assigned to different doses of SR-ISMN (60 and 120 mg of SR ISMN daily) for additional 21 weeks (10 subjects per dose). Patients will continue taking ascorbic acid according to their initial allocation to receive or to not receive vitamin C. The design will therefore be a 2x2 factorial, such that 5 subjects will be allocated to ISMN SR 60- mg without vitamin C, 5 subjects will be allocated to ISMN SR 60- mg with vitamin C, 5 subjects will be allocated to ISMN SR 120- mg without vitamin C, and 5 subjects will be allocated to ISMN SR 120- mg with vitamin C. The intervention will be open label, but endpoint assessments will be blinded.

C.6. 12-week visit

The 12-week visit will take place in which we will perform:

- An office BP measurement
- Arterial tonometry and VaSera measurements
- A 2d Echocardiogram
- 24 hour ambulatory BP monitoring and pulse wave analysis monitoring
- A blood draw and urine sample

C.7. Final (24-week) assessments:

After the end of the 24 weeks therapy, arterial tonometry, VaSera measurements, Doppler echocardiography, cardiac MRI, 24-hour BP / pulse wave analysis monitoring, and blood draws will be repeated after the end of 21 weeks of fixed dose ISMN SR therapy (with or without vitamin C), to assess for changes in response to the study intervention. Procedures will be identical to those performed during the baseline assessment.

C8. Adverse Event Reporting

Targeting Central Hemodynamics in CKD Pilot Study
Protocol Version 003, February 15, 2016

All adverse events will be reported following institutional guidelines. The research team will keep a log of all adverse events that occur in the trial, and any reportable events will be handled accordingly. The study team in charge of the conduct of the trial is up to date on all trainings pertaining to safety guidelines and adverse event reporting. All Serious Adverse Events will be reported to the site review boards, the Data Safety Monitoring Board, as well as the NIH in a timely fashion.

C.7. Data Management

The data for this trial will be collected by the research staff during each visit that the subject attends. Specific forms have been developed for the questions in this trial and will be filled out via pen and paper. Later, this data will be entered into a database developed in RedCap.

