All data collected in this trial will be housed inside of a locked cabinet in the office space of the research staff, located at Ravdin 2 (Cardiovascular Institute).

C.8. Early termination

Subjects who withdraw due to intolerable adverse events or other safety concerns, or simply because they no longer wish to participate in the trial, will undergo a termination visit in which we will document: (1) vital signs; (2) compliance with the medications, including pill count; (3) Adverse effects. (4) specific reason for withdrawal.

D. Statistical Considerations

All study outcomes are continuous measures, thus, least-square regression models will be used to estimate effect sizes associated with each intervention. For the run-in phase, we will use mixed models to assess within subject changes to 30- 60 and 120 mg, and also to assess the effect of ascorbic acid on this response.

Analysis of the changes at 24 weeks between the study arms will also be assessed with mixed models to assess the following: (1) whether there are any significant within group changes in the outcome measures (from baseline to the final visit) in response to nitrate therapy at 30, 60 or 120 mg; (2) To test whether the outcome improvement in response to combination therapy is different between the 2 doses; (3) Whether vitamin C appears to have any effect on the responses. We recognize that this is a pilot study and therefore we will pay particular attention to the variability in the response and will interpret trends conservatively, particularly when confidence intervals are wide enough to be inconclusive. We note that, even though there is limited power for the inferential analyses, the data from this study will be critical to perform power calculations and propose a definitive trial, as per the aims of our R56 award. MRI endpoints will involve only 2 measures (baseline Targeting Central Hemodynamics in CKD Pilot Study

Protocol Version 003, February 15, 2016

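### Inclusion criterion 3 sets no limit on partial dose reductions and omits hydralazine and statins, so a subject with recently changed background therapy can enter as stable

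*Combined protocol and SAP*

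**What the plan says.** Section C.3 gives two adjacent inclusion criteria on background drugs.

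- Criterion 3, on stability: "3) Stable medical therapy as defined by no addition, removal or change in dosage >100% of ACE" and, continuing, "inhibitors, angiotensin receptor blockers, beta-blockers, or calcium channel blockers for >30 days". It does not say which dose is the reference for the percentage.
- Criterion 4, on nitrate tolerance: "4) Current therapy with an ACE inhibitor, hydralazine or a statin, all of which have been shown to reduce nitrate tolerance". Any one of the three is enough. No minimum duration or dose stability is attached to it.

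The design gives every subject the nitrate. In Section C.5, "After baseline assessments, ISMN will be initiated at a dose of 30 mg daily (with or without ascorbic acid"), and the dose then rises through 60 to 120 mg at roughly weekly steps. After the run-in, "subjects will be assigned to different doses of SR-ISMN (60 and 120 mg of SR ISMN daily) for additional 21 weeks (10 subjects per dose"). Vitamin C, yes or no, is the other factor.

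The primary aims concern variability of change. The first reads "To assess the variability in the change in LV mass with ISMN administration", and the others apply the same idea to fibrosis and to systolic and diastolic function. The first question listed in Section D for the 24-week analysis is "whether there are any significant within group changes in the outcome measures (from baseline to the final visit) in response to nitrate therapy". Its other two questions compare the two doses and examine vitamin C.

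**The concern.** A stability criterion is there so that change after baseline is not the tail of a drug adjustment made before baseline. As written, this one has two gaps. Its dose limit appears to work in one direction only, and its class list does not match the list that the next criterion relies on.

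The protocol itself gives reasons why background drugs matter here. Section B says that standard antihypertensive therapy alters wave reflections unpredictably, and cites an observational study in which a fall in wave reflections went with LV mass regression. Criterion 4 names hydralazine and statins because they modify nitrate tolerance. The drugs left uncontrolled can therefore act on the quantities being measured.

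Three outputs are exposed, because no nitrate-free group exists against which drift could be subtracted: the within-group changes from baseline, the run-in dose-response, and the variability estimates intended for planning the definitive trial.

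**Working it through.** **Inputs, all from Section C.3.** Limit: a dosage change strictly above 100%, with addition and removal barred separately. Classes in criterion 3: ACE inhibitors, ARBs, beta-blockers, calcium channel blockers. Classes in criterion 4: ACE inhibitor, hydralazine, statin.

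**Step 1: what the limit catches, measured against the prior dose.** Percent change = 100 × |new − old| / old.

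| Change | Percent change | Above 100%? | Barred by criterion 3? |
|---|---|---|---|
| Cut to three quarters | 100 × 1/4 = 25 | no | no |
| Halving | 100 × 1/2 = 50 | no | no |
| Cut to one quarter | 100 × 3/4 = 75 | no | no |
| Cut to one hundredth | 100 × 99/100 = 99 | no | no |
| Complete stop | 100 × 1/1 = 100 | no | yes, as a removal |
| Exact doubling | 100 × 1/1 = 100 | no | no |
| 2.5 times | 100 × 3/2 = 150 | yes | yes |
| Tripling | 100 × 2/1 = 200 | yes | yes |

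In general, for any new dose above zero and below the old one, |new − old| / old = 1 − new/old, which is less than 1. No partial reduction can reach the limit, whatever its size.

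**Step 2: do other readings close the gap?**

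- With the limit read as 100% or more, a doubling is caught, but every partial reduction still passes.
- With the new dose as denominator, halving gives 100 × 1/1 = 100% and passes, while a cut to one quarter gives 100 × 3/1 = 300% and is caught. But a doubling is then 50% and a tripling 66.7%. An increase equals 1 − old/new, which is always below 1, so no increase could be caught.

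Under each reading, one direction is left wholly unlimited.

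**Step 3: class lists side by side.** Criterion 4 classes absent from criterion 3: hydralazine and statin, two of three. A subject who qualifies through either drug alone may have started it the day before. A subject who qualifies through an ACE inhibitor is covered for starting and stopping that drug, but hydralazine or a statin may still have been added or withdrawn alongside it. No other section adds a stability rule for these two drugs.

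**Step 4: where drift would go.** Suppose a share p of subjects carries residual drift d after baseline, unrelated to their response to ISMN.

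- Mean change from baseline shifts by p × d. If drifts differ in sign, they partly cancel here.
- Variance of change rises by p(1 − p)d². Opposite signs do not cancel in the variance.
- In the run-in, every subject takes 30, 60 and 120 mg in that order. Drift over those three weeks cannot be separated from a dose effect.
- In the 60 versus 120 mg and vitamin C contrasts, random assignment makes the expected difference in drift zero. Added variance and chance imbalance remain, with 20 subjects and 5 per cell.

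The documents give neither p nor d, nor an SD of change for any endpoint, so these expressions cannot be turned into a figure. As headcounts only, one such subject is 1/20 = 5% of the sample and 1/5 = 20% of a cell.

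**The case against.** The case against giving this much weight has several parts.

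- **Baseline follows the change.** Baseline is measured after any pre-entry adjustment, so part of the effect is already in it. This stands: only the residual drift counts.
- **One class is enough for criterion 4.** This also stands. Not every subject depends on an unlisted drug, and the documents show only that such subjects can enter, not that they will.
- **It is a pilot.** Section D admits limited power and promises cautious interpretation. Caution does not remove drift from a variance estimate or from a fixed dose sequence, and those are what the pilot is meant to deliver.
- **The entry rule is a partial remedy.** The documents also state no handling of background drug changes during the 24 weeks. That is true and a separate matter; it does not justify an entry rule that misses partial reductions.

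A reader might also infer more than the text supports:

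- *That letting an exact doubling through is an error.* Tolerating one doubling may be deliberate, to allow ordinary titration, and nothing in the protocol says a doubling should disqualify.
- *That diuretics are wrongly left out.* Neither criterion relies on them and the protocol does not raise them as a stability concern. The case for hydralazine and statins rests on criterion 4.
- *That the randomized comparisons are biased.* Dose and vitamin C are randomly assigned, so a pre-entry change does not favour one group in expectation.
- *That a blood pressure shift, or an inflation of the definitive trial's sample size, can be quoted.* Any such figure would need assumed inputs, and a blood pressure illustration would not carry over to the primary MRI and echocardiographic endpoints.

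**Conclusion.** The concern holds in a limited form. Read against the prior dose, criterion 3 catches no partial dose reduction, and it omits two of the three classes that can satisfy criterion 4. The first statement depends on the prior dose being the denominator, which is the usual reading but is not stated; the alternative leaves increases unlimited instead. The second depends on no assumption.

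The consequence is that subjects in the middle of a drug adjustment can enter as stable. Any residual drift would be attributed to ISMN in the uncontrolled within-group and run-in analyses, and would widen the variability estimates if it is unrelated to the response to ISMN. The randomized contrasts lose precision but are not biased in expectation. The numerical effect is unknown and may be small. The amendment is worth making because it is cheap and the exposed quantities are the pilot's stated products, not because a large distortion has been shown.

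**What to change.** Amend inclusion criterion 3 in Section C.3 in three respects:

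1. State the reference dose for the percentage.
2. Limit dose changes in both directions. The sponsor sets the threshold and says explicitly whether a doubling counts as a change.
3. Reconcile the class list with criterion 4 by applying the same requirement of more than 30 days' stability to hydralazine and statins.

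This is a change to a single criterion. The cost is that some candidates wait up to 30 days before they qualify; the documents give no recruitment data from which to say how many.

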Exclusion Criteria: (1) A clinically- indicated stress test demonstrating significant myocardial ischemia within 1 year of enrollment, not followed by coronary revascularization; (2) Rhythm other than sinus (i.e., atrial fibrillation); (3) Non-cardiac condition limiting life expectancy to <1 year; (4) Current or anticipated future need for long acting organic nitrate therapy; (5) Severe aortic or mitral valve disease; (6) Hypertrophic cardiomyopathy; (7) Known infiltrative or inflammatory myocardial disease (amyloid, sarcoid); (8) Pericardial disease; (9) Primary pulmonary arteriopathy; (10) History of myocardial infarction, unstable angina, percutaneous transluminal coronary angiography (PTCA) or coronary artery bypass grafting (CABG) within 60 days, or requirement for either PTCA or CABG at the time of consent; (11) Resting heart rate (HR) >100 bpm; (12) A reduced LV ejection fraction (EF<50%); (13) Known severe liver disease (AST >3x normal, alkaline phosphatase or bilirubin >2x normal); (14) Allergy to ISMN; (15) Current therapy with phosphodiesterase inhibitors, such as sildenafil, vardenafil or tadalafil, since the combination of ISMN and phosphodiesterase inhibitors can result in severe hypotension; (16) Therapy with rosiglitazone, since its combination with ISMN is not recommended; (17) Current pregnancy or a positive urine pregnancy test; women who become pregnant during the study will be discontinued from the trial; (18) Therapy with warfarin (as vitamin C may interact with warfarin);^{54, 55} (19) History of kidney stones (as vitamin C may increase the excretion of oxalate); (20) History of G6PD deficiency (as vitamin C may precipitate hemolysis in these patients);^{54, 55} (21) Systolic blood pressure <110 mmHg or diastolic blood pressure <40 mmHg; (22) Contraindications to a cardiac MRI: (a) Central nervous system aneurysm clips; (b) Implanted neural stimulators; (c) Implanted cardiac pacemaker or defibrillator; (d) Cochlear implant; (e) Ocular foreign body (e.g. metal shavings); (f) Other implanted medical devices: (e.g. drug infusion ports); (g) Insulin pump; (h) Metal shrapnel or bullet; (i) Claustrophobia; (j) Extreme obesity rendering the patient unable to fit into narrow-bore scanners; (k) Unwillingness of the patient to undergo a cardiac MRI.

Flow of subjects in the study.

C.4. Baseline assessments

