c. Protection against risks associated with gadolinium contrast: Serum creatinine will be measured prior to each scan to assure adequate renal function for the administration of gadolinium-based contrast as per our inclusion/exclusion criteria. Pregnancy status will be determined for all women of childbearing age before enrollment and before the final MRI scan. Pregnant women will be excluded and/or discontinued from the study. Subjects will not receive two injections of gadolinium within one week of each other as frequent use of gadolinium can cause nephrogenic systemic fibrosis (NSF). If a subject has recently received an MRI for clinical purposes, the research MRI will be delayed to avoid the second injection of gadolinium within the one week-timeframe.

d. Protection against risks of study medications: To reduce the risk of hypotension and related side effect, participants will be instructed to get up slowly when rising from a sitting or lying position. The study team will specifically assess for the presence of Targeting Central Hemodynamics in CKD Pilot Study

Protocol Version 003, February 15, 2016

hypotension and orthostatic hypotension, as well as symptoms such as dizziness after the medication is initiated or after the dose is increased, in order to determine whether it is safe for participants to continue taking these medications, or to uptitrate the dose. If participants find these side effects too uncomfortable, they will be deemed intolerant to the drugs and discontinued from the study. Study subjects can always withdraw from the study at any time and this will be made clear to them. We will specifically exclude individuals who are taking sildenafil (Viagra®), tadalafil (Cialis®), or vardenafil (Levitra®) and we will instruct them not to take these medications while participating in the study, as well as the risks associated with this combination. If subjects express the wish to take these medications within the 24 weeks following consent, they will not be included in the study. We will exclude subjects with a history of kidney stones, since vitamin C may precipitate the recurrence of oxalate kidney stones. We will also exclude patients with G6PD deficiency, since vitamin C may precipitate hemolysis in this condition.^{72, 73}

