dose of IMDUR Tablets demonstrated a significant increase in total treadmill time at 4 and 12 hours post dosing, but by day 42, the 30 and 60 mg doses no longer were differentiable from placebo. Throughout chronic dosing, rebound was not observed in any IMDUR treatment group. Pooled data from two other trials, comparing IMDUR Tablets 60 mg once daily, ISDN 30 mg QID, and placebo QID in patients with chronic stable angina using a randomized, double-blind, three-way crossover design found statistically significant increases in exercise tolerance times for IMDUR Tablets compared to placebo at hours 4, 8 and 12 and to ISDN at hour 4. The increases in exercise tolerance on day 14, although statistically significant compared to placebo, were about half of that seen on day 1 of the trial.

INDICATIONS AND USAGE

IMDUR Tablets are indicated for the prevention of angina pectoris due to coronary artery disease. The onset of action of oral isosorbide mononitrate is not sufficiently rapid for this product to be useful in aborting an acute anginal episode.

CONTRAINDICATIONS

IMDUR Tablets are contraindicated in patients who have shown hyper sensitivity or idiosyncratic reactions to other nitrates or nitrites.

WARNINGS

Amplification of the vasodilatory effects of IMDUR by sildenafil can result in severe hypotension. The time course and dose dependence of this interaction have not been studied. Appropriate supportive care has not been studied, but it seems reasonable to treat this as a nitrate overdose, with elevation of the extremities and with central volume expansion. The benefits of ISMN in patients with acute myocardial infarction or congestive heart failure have not been established; because the effects of isosorbide mononitrate are difficult to terminate rapidly, this drug is not recommended in these settings.

If isosorbide mononitrate is used in these conditions, careful clinical or hemodynamic monitoring must be used to avoid the hazards of hypotension and tachycardia.

PRECAUTIONS

General

Severe hypotension, particularly with upright posture, may occur with even small doses of isosorbide mononitrate. This drug should, therefore, be used with caution in patients who may be volume depleted or who, for whatever reason, are already hypotensive.

Hypotension induced by isosorbide mononitrate may be accompanied by paradoxical bradycardia and increased angina pectoris. Nitrate therapy may

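### Exclusion 14 does not carry over the appended label's only contraindication, a past reaction to another nitrate or nitrite: a small, safety-only gap that one line would close

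*Combined protocol and SAP*

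**What the plan says.** Section C.3 lists 22 exclusion criteria. The one that deals with a reaction to the study nitrate is "14) Allergy to ISMN".

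Appendix I reproduces the prescribing information for the product. Its Contraindications heading holds one sentence: "IMDUR Tablets are contraindicated in patients who have shown hyper sensitivity or idiosyncratic reactions to other nitrates or nitrites".

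Other cautions from the same label do reach the eligibility rules. Under Warnings the label says "Amplification of the vasodilatory effects of IMDUR by sildenafil can result in severe hypotension"; C.3 excludes users of phosphodiesterase inhibitors (criterion 15), and F.2.d repeats it: "We will specifically exclude individuals who are taking sildenafil".

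On starting treatment, C.5 says "After baseline assessments, ISMN will be initiated at a dose of 30 mg daily". The first visit afterwards comes "after ~1 week (5-9 days). ISMN will be increased to 60 mg daily". Appendix II lists a medical history and the handing out of medication at the same baseline visit.

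**The concern.** An eligibility list normally takes in at least the contraindications of the drug being given. Here the label's one formal contraindication is absent, while several of its lesser cautions are present. No reason is given, so this looks like an oversight rather than a choice.

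What is at stake is the safety of an individual participant. Section G.1 calls an allergic reaction very rare, but the manifestations it names include trouble breathing and swelling of the throat. Section F.3 anticipates no direct benefit to participants, so nothing offsets exposing someone whom the label would not treat. The estimates of variability and dose response, which are the purpose of the pilot, are not touched.

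**Working it through.** No arithmetic bears on the gap itself. The check sets the texts side by side and asks whether anything else in the protocol catches the patient in question.

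1. **What each text covers.**

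| | C.3, criterion 14 | Appendix I, Contraindications |
|---|---|---|
| Agent | ISMN | nitrates or nitrites other than ISMN |
| Reaction | allergy | hypersensitivity or idiosyncratic reaction |

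Read literally, the two name different agents, and the label also names a type of reaction that the word allergy does not plainly include.

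2. **Could another C.3 criterion catch the patient?**
- The only other criterion naming the nitrate class is "4) Current or anticipated future need for long acting organic nitrate therapy". It concerns need for treatment, not a past reaction.
- Patients with coronary disease are the ones most likely to have met a short-acting nitrate. The relevant rule is "10) History of myocardial infarction, unstable angina, percutaneous transluminal coronary angiography (PTCA) or coronary artery bypass grafting (CABG) within 60 days" (or a need for either procedure at consent), so older events are allowed. Criterion 1 (ischemia on a stress test within a year) does not apply once revascularization has followed.
- There is no criterion for any contraindication to study drug and none for investigator discretion. Criterion 22 is a contraindication list, but for cardiac MRI only.

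3. **Could the safety sections catch the patient before dosing?** The eligibility protections in F.2.d name phosphodiesterase inhibitors, kidney stones and G6PD deficiency. F.1 mentions allergy only as a rare side effect. Neither asks about earlier reactions to nitrates.

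4. **Which label cautions were carried over?** Phosphodiesterase inhibitors (criterion 15; the label's Warnings name sildenafil), low blood pressure (criterion 21; Precautions) and hypertrophic cardiomyopathy (criterion 6; Precautions). The single Contraindications entry was not.

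5. **What happens if the patient is enrolled?** ISMN is given out at baseline and no observed first dose is described. The safeguards are:
- checks for hypotension, orthostatic hypotension and symptoms such as dizziness after initiation or a dose increase (F.2.d);
- blood pressure and symptom conditions for up-titration (C.5);
- discontinuation for intolerance (C.5 and F.2.d);
- adverse event monitoring at visits and calls (G.1), with the timing of calls not given.

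All of these act after exposure. The first two are aimed at vasoactive effects rather than allergy.

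6. **What must a reworded rule avoid?** It must not exclude everyone who once had a headache on a nitrate. The label's adverse event table gives these rates at the study doses:

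| | Placebo | 30 mg | 60 mg | 120 mg |
|---|---|---|---|---|
| Headache | 15% | 38% | 51% | 42% |
| Excess over placebo, points | – | 38 − 15 = 23 | 51 − 15 = 36 | 42 − 15 = 27 |
| Dizziness | 4% | 8% | 11% | 9% |
| Excess over placebo, points | – | 8 − 4 = 4 | 11 − 4 = 7 | 9 − 4 = 5 |

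These figures support an allowance for expected effects. They say nothing about how often the gap would matter.

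**The case against.** The other side has a fair case. The contraindication is physically in the protocol, in Appendix I. The principal investigator is a cardiologist working with a nephrologist and hypertension expert, and a history is taken at the visit where drug is given out. Appendix I describes ISMN as an organic nitrate, so a chart entry of general nitrate allergy could well be read as meeting criterion 14. Section B says nitrates are not routine therapy in CKD or hypertension, and the protocol calls allergy to the drug very rare. What remains is mainly a patient, among 20, whose recorded reaction names a different nitrate or nitrite.

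All of that stands as mitigation and keeps the point minor. It does not close the gap: nothing says that the label overrides C.3, and a clinician applying the written list would find no criterion to cite.

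Two stronger readings are tempting and should be resisted:
- A reader might infer that criterion 14 is a narrower version of the label's rule. It is not, because the label sentence speaks of other nitrates and criterion 14 of ISMN, so neither contains the other. The accurate statement is that the label's entry was not carried over.
- A reader might size the risk by multiplying the daily dose by the days to the first visit. That assumes a reacting patient keeps taking the drug, whereas someone with hives or throat swelling would be expected to stop. In any case, cumulative dose does not measure allergic harm.

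**Conclusion.** The point holds as a gap in eligibility wording. A patient with a recorded reaction to a different nitrate or nitrite, and no ISMN allergy, meets no written exclusion on that ground and could be given the drug at baseline although the appended label contraindicates it.

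Its size is small. The documents give no rate of prior reactions to other nitrates, so the chance of enrolling such a patient among 20 cannot be computed; the protocol's own statements suggest that it is low. The documents do not support a claim that the trial is unsafe overall or that any result would be biased. The conclusion assumes that C.3 is the operative eligibility list and is applied as written. It warrants a cheap improvement, made before the wording is carried into the larger trial that the sponsor plans.

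**What to change.** Reword criterion 14 along these lines: *Allergy, hypersensitivity or idiosyncratic reaction to ISMN or to any other nitrate or nitrite (common expected effects such as headache or mild dizziness do not count; prior severe hypotension or syncope on a nitrate does).* The second half of the bracket is needed because the label warns that severe hypotension can follow even small doses, and without it staff could not tell whether such a history counts as expected.

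Ask the question in the medical history already scheduled at baseline, before medication is given out.

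The cost is one line in C.3 and one question, with no new visit or procedure. The downside is a very small loss of eligible patients, which the allowance for expected effects helps to limit.
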